9.10.33. WHO/NYHA Functional Class Assessment

WHO functional class assessment (Section 20, Appendix 2) will be made and documented at the time points indicated in [Table 3](#) or [Table 4](#) and [Table 5](#) or [Table 6](#) as well as at any time clinical worsening is suspected. WHO/NYHA FC will be assessed. To the extent feasible, the same evaluator should assess WHO/NYHA FC for a particular patient over the entire course of the study.

9.10.34. Pharmacokinetic (PK) Blood Samples

Blood samples for determination of plasma bardoxolone methyl and potential metabolite concentrations will be drawn at the time points indicated in [Table 3](#) or [Table 4](#) and [Table 5](#) or [Table 6](#). Patients will be asked by site personnel to provide the time of their last two study drug administrations prior to the blood samples being collected. This data will be based on patient recall and not collected in a patient diary. Blood sample collection instructions should be referenced in the laboratory manual.

The date and time of collection of all PK blood samples should be recorded; however, any deviations from the protocol-specified sampling times will not be considered protocol deviations. Sample time deviations will be summarized in the study report. Dates in the case report form should be recorded in an unambiguous format (e.g., DD MMM YYYY) and time should be recorded to the nearest minute (e.g., HH:MM using the 24-hour clock). Blood samples not drawn should be recorded as such.

[REDACTED]

[REDACTED]

[REDACTED]

9.10.38. High Resolution Computed Tomography (HRCT) Scan or Biopsy

A HRCT scan or biopsy to confirm presence of ILD must be completed prior to Day 1 is required for patients to enroll in Cohort 4. However, if a patient has not had a HRCT scan or biopsy completed prior to planned Day 1, it should be performed after the patient has signed Informed Consent and has passed the Screen A eligibility procedures.

[REDACTED]

[REDACTED]

[REDACTED]

[REDACTED]

[REDACTED]

[REDACTED]

10. STUDY DRUG MATERIALS AND MANAGEMENT

10.1. Study Drug

Bardoxolone methyl capsules, 2.5 mg, 5 mg, 10 mg, and 15 mg, and placebos to match, will be used in this study.

10.2. Study Drug Packaging and Labeling

Kits will be dispensed during study Part 1 (Day 1 through Week 12 dispensing). Either bottles containing 30-count or 90-count of capsules or treatment kits will be dispensed during study Part 2. The extension period begins with the Week 16 dispensing. The blind will be maintained until the Week 20 dispensing.

During study Part 1, the study drug will be supplied in tamper-evident kits containing three 30-cc high-density polyethylene (HDPE) bottles and one 60-cc HDPE bottle. Each bottle will utilize foil induction-seal liners and a child-resistant closure. Each bottle of study drug will contain 30 count of 2.5 mg, 5 mg, or 15 mg strength bardoxolone methyl or corresponding placebo capsules. Each bottle will also contain a desiccant insert that must not be ingested. Labeling on each kit bottle will contain the following information:

- Medication ID number;
- Protocol 402-C-1302;
- Caution Statement: Limited to Investigational Use. Keep out of sight or reach of children;
- Store at 20° – 25°C (68° – 77°F), excursions allowed to 15° – 30°C (59° – 86°F);
- Reata Pharmaceuticals, Inc., Irving, TX.

During study Part 2, the study drug may also be supplied in 30-count or 90-count bottles with child-resistant closures. Additionally, labeling, in the relevant local languages for investigational medicinal product (IMP) for use and distribution in the EU shall adhere to current Eudralex, Volume 4 Annex 13 guidance and requirements.

10.3. Study Drug Storage

The stability of the drug product is being evaluated in ongoing studies.

Investigative sites must store the investigational product in a secure location with room temperature conditions of 20° - 25°C (68° - 77°F), excursions allowed to 15° – 30°C (59 – 86°F).

10.4. Study Drug Administration

Please refer to Section 9.10.14 for details on study drug administration. Clear instructions will be provided to the patient regarding the number and type of capsules to be ingested at each study drug administration time point listed in Table 3 or Table 4 and Table 5 or Table 6. Patients must be instructed to continue taking study drug once daily up through their Week 16 visits unless otherwise instructed by the Investigator or been formally discontinued from the study. Patients entering the extension period will be instructed to continue taking bardoxolone methyl once daily

through the end of the study unless otherwise instructed by the Investigator or been formally discontinued from the study.

10.5. Study Drug Accountability

The Investigator, or designee, will maintain a record of all study drug received, dispensed, and returned to the Sponsor or its designee. No study drug shall be destroyed by the clinical site unless directed to do so by the Sponsor or its designee. Study drug bottles and any unused capsules should be returned to the study staff.

10.6. Study Drug Handling and Disposal

At the conclusion of the study, the Sponsor or its designee will direct the site regarding the final disposition of any remaining study drug.

11. SAFETY ASSESSMENTS

11.1. Safety Parameters

To avoid inter-observer variability, every effort should be made to ensure that the same individual who made the initial baseline determinations completes all safety assessments. Safety parameters include vital sign measurements, ECG results, 24-hour ambulatory blood pressure monitoring, physical examination results, adverse events, serious adverse events, weight and laboratory test results (clinical chemistry, hematology, urinalysis and microscopy).

11.2. Adverse and Serious Adverse Events

11.2.1. Definition of Adverse Events

11.2.1.1. Adverse Event

An adverse event (AE) is defined as any untoward medical occurrence in a patient regardless of its causal relationship to study treatment. An AE can be any unfavorable and unintended sign (including any clinically significant abnormal laboratory test result), symptom, or disease temporally associated with the use of the study drug, whether or not it is considered to be study-drug related. Included in this definition are any newly-occurring events or previous condition that has increased in severity or frequency since the administration of study drug.

All AEs that are observed or reported by the patient during the study (from time of administration of the first dose at the Day 1 visit until the final visit indicated in [Table 3](#) or [Table 4](#) and [Table 5](#) or [Table 6](#), as appropriate) must be reported, regardless of their relationship to study drug or their clinical significance.

11.2.1.2. Serious Adverse Event

A serious adverse event (SAE) is any AE occurring at any dose and regardless of causality that:

- Results in death;
- Is life-threatening;
- Requires inpatient hospitalization or prolongation of existing hospitalization;
- Results in persistent or significant incapacity or substantial disruption of the ability to conduct normal life functions;
- Is a congenital anomaly or birth defect in an offspring of a patient taking study drug;
- Is an important medical event.

The term "life-threatening" refers to an event in which the patient was at immediate risk of death at the time of the event. It does not refer to an event that hypothetically might have caused death if it were more severe.

Important medical events are those that may not meet any of the criteria defined above, however, they may be considered serious when, based upon appropriate medical judgment, they may jeopardize the patient and may require medical or surgical intervention to prevent one of the other outcomes listed in the SAE definition.

Pregnancy is not considered an AE; however, information will be collected for any pregnancies which occur during the study (from the time of the first dose of study drug until the final visit indicated in [Table 3](#) or [Table 4](#) and [Table 5](#) or [Table 6](#), as appropriate). Certain pregnancy outcomes will require submission as an SAE (See Section [9.8](#)).

The Investigator is responsible for reporting to Reata or designee all AEs and SAEs that are observed or reported by the patient during the study (from the time of administration of the first dose of study drug until the final visit indicated in [Table 3](#) or [Table 4](#) and [Table 5](#) or [Table 6](#), as appropriate), regardless of their relationship to study drug or their clinical significance. All SAEs reported or observed during the study must be followed to resolution or until the Investigator deems the event to be chronic or the patient to be stable. Reata or designee may contact the Investigator to obtain additional information on any SAE which has not resolved at the time the patient completes the study.

11.3. Eliciting Adverse Event Information

At every study visit, patients must be asked a standard, non-directed question, such as, “How have you been feeling since your last visit?” to elicit any medically related changes in their well-being. They may also be asked if they have been hospitalized, had any accidents, used any new medications, or changed concomitant medication regimens (including prescription drugs, over-the-counter medications, vitamins, herbal products, and minerals). Responses must be documented in the source documents.

In addition to patient observations, AEs must be documented for any clinically significant diagnosis resulting from abnormal laboratory test values, physical examination findings, or ECG abnormalities, or from other documents that are relevant to patient safety.

11.4. Assessment of Causality

The Investigator must use the following classifications and criteria to characterize the relationship or association of the study drug in causing or contributing to the AE:

Unrelated: This relationship suggests that there is no association between the study drug and the reported event.

Unlikely: This relationship suggests that the temporal sequence of the event with study drug administration makes a causal relationship improbable and/or other factors also provide plausible explanations.

Possible: This relationship suggests that treatment with the study drug caused or contributed to the AE. That is, the event follows a reasonable temporal sequence from the time of study drug administration, and/or, follows a known response pattern to the study drug, but could have been produced by other factors.

Probable: This relationship suggests that a reasonable temporal sequence of the event with study drug administration exists and, based upon the known pharmacological action of the drug, known or previously reported adverse reactions to the drug or class of drugs, or judgment based on the Investigator’s clinical experience, the association of the event with study drug administration seems likely.

11.5. Assessment of Severity

The Investigator will grade the severity of the AEs as mild, moderate, or severe using the following definitions:

Mild: Symptoms causing no or minimal interference with usual social and functional activities

Moderate: Symptoms causing greater than minimal interference with usual social and functional activities

Severe: Symptoms causing inability to perform usual social and functional activities.

11.6. Recording Adverse Events

All conditions present prior to the administration of the first dose of study drug (Day 1) should be documented as medical history. After the first dose, documentation of adverse events (AEs) shall continue until 30 days following administration of the final dose of study medication, regardless of the relationship of the AE to study drug. Information to be collected includes type of event, date of onset, date of resolution, Investigator-specified assessment of severity and relationship to study drug, seriousness, as well as any action taken.

While an AE is ongoing, changes in the severity (e.g., worsening and improving) should be noted in the source documents, but when documenting the AE, only the total duration and greatest severity should be recorded in the eCRF. AEs characterized as intermittent require documentation of onset and duration.

All drug-related (Possible or Probable, see Section 11.4) AEs and abnormal laboratory test results reported or observed during the study must be followed to resolution (either return to baseline or within normal limits). All other AEs will be followed through the final visit indicated in Table 3 or Table 4 and Table 5 or Table 6, as appropriate.

AEs resulting from concurrent illnesses, reactions to concurrent illnesses, reactions to concurrent medications, or progression of disease states must also be reported. Preexisting conditions (present before the start of the AE collection period) are considered concurrent medical conditions and should NOT be recorded as AEs. However, if the patient experiences a worsening or complication of such a concurrent condition, the worsening or complication should be recorded as an AE. Investigators should ensure that the AE term recorded captures the change in the condition (e.g., “worsening of...”). Any improvement in condition should be documented as per Section 9.10.12.

Each AE should be recorded to represent a single diagnosis. Accompanying signs (including abnormal laboratory test values or ECG findings) or symptoms should NOT be recorded as additional AEs. If a diagnosis is unknown, sign(s) or symptom(s) should be recorded as an AE(s). Changes in laboratory test values or ECG parameters are only considered to be AEs if they are judged to be clinically significant (i.e., if some action or intervention is required or if the Investigator judges the change to be beyond the range of normal physiological fluctuation). If abnormal laboratory test values or ECG findings are the result of pathology for which there is an overall diagnosis (e.g., increased creatinine levels in renal failure), only the diagnosis should be reported as an AE.

Elective procedures (surgeries or therapies) that were scheduled prior to the start of AE collection are not considered AEs. These elective procedures should not be recorded as AEs, but should be documented in the patient's source documents as elective (e.g., elective periodontal surgery). However, if a pre-planned procedure is performed early (e.g., as an emergency) because of a worsening of the preexisting condition, the worsening of the condition should be captured as an AE.

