9.10.6. Right Heart Catheterization

A right heart catheterization (RHC) completed prior to Day 1 is required. However, if a patient has not had a RHC completed prior to planned Day 1, it should be performed after the patient has signed Informed Consent and has passed the Screen A eligibility procedures.

In addition, data resulting from a RHC performed before Day 1 or during the course of the study as part of the patient's standard of care, should be collected on the patient's case report form. Other data resulting from procedures conducted as part of the standard of care for the patient that may contribute to the Sponsor's understanding of the safety or efficacy of the compound may also be requested.

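### AE and SAE collection opens only at first dose, so a serious complication of a protocol-directed screening procedure falls outside SAE collection and 24-hour reporting to the sponsor

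*Protocol*

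**What the plan says.** **When collection opens.** Protocol 11.2.1.1 has AEs reported "from time of administration of the first dose at the Day 1 visit until the final visit indicated in" the schedules. Section 11.2.1.2 sets the same start for the investigator's reporting of AEs and SAEs together: "from the time of administration of the first dose of study drug until the final visit indicated in" those tables. In Tables 3 and 4 the AE row has no entry at screening, and its footnote places the Day 1 assessment after dosing.

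**What happens to earlier events.** Section 11.6 says: "All conditions present prior to the administration of the first dose of study drug (Day 1) should be documented as medical history". It adds: "Preexisting conditions (present before the start of the AE collection period) are considered concurrent medical conditions and should NOT be recorded as AEs". A later worsening or complication of such a condition is recorded as an AE.

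**What counts as serious.** Section 11.2.1.2 builds the SAE on the AE: "A serious adverse event (SAE) is any AE occurring at any dose and regardless of causality that" meets one of the listed criteria. The 24-hour rule in section 11.7 is likewise worded for AEs.

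**What is done before first dose.** If no right heart catheterization exists, section 9.10.6 says "it should be performed after the patient has signed Informed Consent" and after Screen A has been passed. Section 9.10.38 gives the same instruction for Cohort 4 "if a patient has not had a HRCT scan or biopsy completed prior to planned Day 1". Inclusion criterion 7 requires two walk tests on different days before randomization.

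**The SAP.** Section 3.4.5.1 counts Part 1 treatment-emergent events from the first dose. Section 3 summarizes screen failures by reason and leaves them out of its other analyses.

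**The concern.** Starting treatment-emergent AEs at first dose is normal: an event before dosing says nothing about the drug. Here, though, the same start date also governs SAE collection and reporting, and the protocol directs procedures in the interval it leaves uncovered. A catheterization done because the trial needs one is a risk of taking part, even if it is not a risk of bardoxolone methyl.

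If such a procedure causes a serious complication, no clause in section 11 requires an SAE form or a 24-hour report to the sponsor. The patients most seriously harmed may also be the least visible. A hospitalization for cardiac or respiratory symptoms can meet exclusion criterion 10 (clinical instability within 8 weeks of Day 1), so the patient may never be dosed and the AE window never opens. At stake is a complete safety account of trial participation. No efficacy estimate is affected.

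**Working it through.** The plan states no figure for screening complications, so there is nothing to reproduce. The check has two parts.

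**Part 1: the window, step by step**

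1. Consent, then Screen A. Tables 3 and 4 schedule medical history here and nowhere else.
2. Catheterization if none exists; in Cohort 4, HRCT or biopsy if neither exists (sections 9.10.6 and 9.10.38). Both come after Screen A, so after the scheduled medical history entry. The second pre-randomization walk test also falls before dosing.
3. First dose. AE and SAE collection opens after it.

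Screening may last up to 28 days in Cohorts 1 and 2 (Table 3) and up to 60 days in Cohorts 3 and 4 (Table 4).

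The definitions then close off the SAE route. An SAE must be an AE (11.2.1.2). A condition present before first dose is not recorded as an AE (11.2.1.1, 11.6). So a pre-dose complication is not an SAE, and the rule in 11.7 is not triggered. The causality scale in 11.4 covers study drug only and has no category for a procedure.

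**Part 2: how many events**

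Inputs from the documents: 198 patients expected and 486 at most (Protocol 7.2).

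Assumptions, none of which the documents give:
- 30% of screened patients fail screening;
- a share *p* of 10–30% of those reaching this stage need a procedure;
- a serious complication rate *r* of 0.5–2% per procedure.

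Formula: expected events = N reaching the procedure stage × *p* × *r*.

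The procedures follow a passed Screen A, so N depends on when failures occur. If all occur at Screen A, N is the number enrolled. If all occur later, N is the number screened: 198/0.7 = 283, or 486/0.7 = 694.

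| Enrolled | Screen failures | N | Procedures (10–30%) | Events (0.5–2%) |
|---|---|---|---|---|
| 198 | all at Screen A | 198 | 20–59 | 0.1–1.2 |
| 198 | all after Screen A | 283 | 28–85 | 0.1–1.7 |
| 486 | all at Screen A | 486 | 49–146 | 0.2–2.9 |
| 486 | all after Screen A | 694 | 69–208 | 0.3–4.2 |

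For example, 198 × 0.10 × 0.005 = 0.10 and 198 × 0.30 × 0.02 = 1.19; 694 × 0.30 × 0.02 = 4.2.

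One rate is applied to every procedure and cohort. That is crude: HRCT is non-invasive, and the HRCT/biopsy rule covers only Cohort 4 (4 × 24 = 96 of 198 planned patients). Walk-test complications are not counted.

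**The case against.** The best case for the plan is that it is consistent. Sections 11.2.1.1, 11.2.1.2 and 11.6, the schedules and the SAP agree on first dose as the start, and no analysis depends on earlier events. That stands: this is a design choice with a gap, not a contradiction.

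A reader might go further and infer that these events are never reported to anyone, or leave no trace. The documents do not support that.

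- Section 15.5 keeps a general investigator duty to tell the IRB/EC about problems that put patients at risk, with no first-dose limit. It does not create an SAE report to the sponsor.
- For a patient who goes on to dosing, the event should enter medical history under 11.6. Physical examination is repeated on Day 1, with changes since Screening classified (9.10.12). SAP 3.4.3 has medications recorded from 28 days before first dose, and SAP 2.3 puts all eCRF data in by-patient listings.
- SAP section 3 decides who enters the analyses. Leaving screen failures out of tables does not by itself stop a safety report.
- The PSRC's main task is dose-level safety and then the safety of enrolled patients (9.6.3). An event before randomization has no treatment arm and cannot inform dose selection, so a loss to the PSRC is a weak argument.

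The exposed group is also limited. A documented catheterization is an entry criterion, so one at screening is the fallback; Table 3 accepts one up to 36 months old. Nothing requires biopsy, since HRCT suffices and section 8.1 admits unclassifiable idiopathic interstitial pneumonia without a lung biopsy.

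In the other direction, section 11.3 asks the open AE question at every study visit, which might seem to cover screening. Sections 11.2.1.1 and 11.2.1.2 and the schedules still confine collection to the period after first dose.

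**Conclusion.** The gap is real but narrow. As written, no clause sends a serious complication of a protocol-directed screening procedure into SAE collection or to the sponsor within 24 hours. It matters most for patients who then fail screening and are never dosed, because the AE window does not open for them and the general IRB/EC duty is the only route the protocol leaves. The reading that such harm goes entirely unrecorded is too strong, for the reasons above.

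The expected count is small: about 0.1–1.2 events at 198 enrolled and 0.2–2.9 at 486 if all screen failures occur at Screen A, with upper limits of 1.7 and 4.2 if they all occur later. These figures rest wholly on the assumed failure, procedure and complication rates. The reading of the collection window does not depend on them. The point merits a low-priority correction because each event would be serious and the remedy is cheap.

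**What to change.** Amend Protocol 11.2.1.1, 11.2.1.2, 11.6 and 11.7, and the AE rows and footnotes of Tables 3 and 4, so that SAEs related to protocol-required procedures are collected and reported to the sponsor from informed consent, including in patients who fail screening. State in 11.6 that such an event is reported as an SAE even though it precedes first dose.

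In the SAP, keep the treatment-emergent window at first dose and add a separate listing of pre-dose SAEs that includes screen failures.

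The cost is amendment wording and a few additional SAE forms. Sample size, efficacy analyses and treatment-emergent AE tables do not change.

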Cohorts 3 and 4 patients randomized to placebo in study Part 1 will be assigned to 5 mg of bardoxolone methyl, whereas, patients randomized to bardoxolone methyl in study Part 1 will begin study Part 2 (Week 16) at the same dose of bardoxolone methyl as they ended with in study Part 1. All patients in Cohorts 3 and 4 will have the option to up-titrate their dose at the Week 20 visit, and may de-escalate in dose (minimum dose of 2.5 mg) at scheduled or unscheduled visits. Treatment assignment will remain blinded for Cohort 3 and 4 patients through Week 20.

Treatment-compliant patients who have completed Part 2 of the study are eligible to continue receiving bardoxolone methyl through an extended access program (Study 402-C-1602). After Week 32, visits will occur every 24 weeks until bardoxolone methyl is available through the extended access program. Once bardoxolone methyl is available through the extended access program, patients in Part 2 who have completed at least 32 weeks of the study will complete an End of Treatment Visit. The Week 32 visit may be the same as the End of Treatment Visit. Beginning with the Week 32 visit, patients will be seen in the clinic every 24 weeks (i.e., Week 56, Week 80, Week 104, etc.) and receive a 6-month supply of study drug at the appropriate dose.

The Sponsor reserves the right to stop the study for a given cohort if development of bardoxolone methyl is discontinued for any reason, or if the assessment of available data raises concerns about the safety or efficacy of bardoxolone methyl.

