#### 3.4.5.1 Part 1 Treatment Emergent Adverse Events

The Medical Dictionary for Regulatory Activities (MedDRA) dictionary will be used to classify all adverse events reported during the study by system organ class (SOC) and preferred term

(PT). Analysis of treatment-emergent adverse events from Part 1 (Part 1 TEAE) will include all new or worsening adverse events with date of onset during or after the date of first study drug administration through the end of Part 1. Part 1 TEAE summaries will exclude adverse events with date of onset after the Week 16 visit date or date of onset more than 30 days after the date of last study drug administration for patients who discontinue treatment. Part 2 TEAE summaries will exclude adverse events with date of onset more than 30 days after the date of last study drug administration for patients who discontinue treatment. Adverse events will be summarized by SOC and PT. Tables and listings will summarize adverse events occurring in Part 1 and 2 separately. Drug-related AEs, SAEs, and serious drug-related AEs will be summarized accordingly. Multiple occurrences of the same event will be counted once for each patient at the level of SOC and the level of PT.

Adverse events by SOC, PT, and severity will also be summarized. Multiple occurrences of the same event will be counted once for each patient by preferred term under the highest severity.

In the presence of partial dates, the available data (month and/or year) will be compared to the appropriate study reference dates to identify the most likely study period.

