### 3.5.5 Safety

Safety analyses described in Section 3.4.4 will be performed on available safety data from Part 2 using the Part 2 treatment groups (BARD, PBO-BARD). Change from baseline summaries of safety described in 3.4.3 will include both change from baseline (Part 1) and change from the end of Part 1 (Week 16) for Part 2.

Analyses of adverse events will count only Part 2 treatment-emergent adverse events (TEAEs), defined as new or worsened events after the Week 16 visit. New or worsened events after Week 16 visit are those events with an AE start date after the Week 16 study visit, or previously recorded AEs with an adverse change in severity (e.g., went from mild to moderate or moderate to serious) after the Week 16 study visit. Similarly, only new onset concomitant medications (date of first dose after the Week 16 visit) will be included in Part 2 summaries.

Shift tables will be provided to assess changes from normal to abnormal shifts from Week 16 to each nominal visit for chemistry and hematology parameters.

Additional details will be provided in the mock Tables, Listings, and Figures.

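### The eCRF severity rule in Protocol 11.6 does not supply what the SAP needs to split adverse events between Part 1 and Part 2 at Week 16

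*Protocol*

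**What the plan says.** **Recording.** Protocol 11.6 has the site follow an ongoing event in two places. In the first, "changes in the severity (e.g., worsening and improving) should be noted in the source documents". In the second, "when documenting the AE, only the total duration and greatest severity should be recorded in the eCRF". On the fields themselves: "Information to be collected includes type of event, date of onset, date of resolution, Investigator-specified assessment of severity and relationship to study drug", followed by seriousness and action taken. A separate record for worsening is provided for one case only, conditions that existed before AE collection began: "Preexisting conditions (present before the start of the AE collection period) are considered concurrent medical conditions", and their later worsening is entered as a new AE.

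**Part 1 tables.** SAP 3.4 limits Part 1, for patients who go on to Part 2, to data up to and including the Week 16 visit. SAP 3.4.5.1 sorts by onset: "Part 1 TEAE summaries will exclude adverse events with date of onset after the Week 16 visit date". In the severity table, multiple occurrences of an event are "counted once for each patient by preferred term under the highest severity".

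**Part 2 tables.** SAP 3.5.5 counts events that start after the Week 16 visit and also "previously recorded AEs with an adverse change in severity (e.g., went from mild to moderate or moderate to serious") after that visit. Results are shown as BARD and PBO-BARD.

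**What happens at Week 16.** In Cohorts 3 and 4, "patients randomized to placebo in study Part 1 will be assigned to 5 mg of bardoxolone methyl" (Protocol 7.1). Placebo patients in Cohorts 1 and 2 move to their group's bardoxolone dose.

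**The concern.** The Week 16 visit is where placebo patients first receive bardoxolone, so the safety tables depend on placing each grade on the correct side of it. An event that straddles the visit needs at least two facts: its grade at Week 16, and whether or when it rose later. Protocol 11.6 sends those facts to the source documents and puts one onset date and one peak grade in the eCRF.

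At stake are AE intensity, which is a safety endpoint (Protocol 6.2.2), and the secondary objective of safety and tolerability against placebo over 16 weeks. The weeks just after the switch matter most. Protocol 5.1.2 reports that in an earlier trial the excess risk of fluid overload and heart failure appeared limited to the first three to four weeks of treatment. Protocol 9.1.1 repeats close weight monitoring at the start of Part 2 for this reason.

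**Working it through.** The plan gives no figure to reproduce. The check is a trace of one event, followed by a scale calculation.

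**Trace (illustrative).** A placebo patient has mild oedema from Week 10. At Week 18, on bardoxolone, it reaches a higher grade.

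1. eCRF under Protocol 11.6: one record, onset Week 10, severity equal to the Week 18 peak. The Week 16 grade and the date of change are in source documents only.
2. Part 1 table under SAP 3.4.5.1: onset is before the Week 16 visit, so the event is kept under placebo. The severity available is the peak. If the record was updated before the data cut, a Week 18 grade stands in a Part 1 table, against the Week 16 limit in SAP 3.4. If it was not yet updated, the Part 1 entry shows the earlier grade and is correct.
3. Part 2 table under SAP 3.5.5: the start date does not qualify. The worsening clause should qualify it, but needs a change in grade after Week 16, and the record shows a single grade. The rule cannot be triggered from these fields.
4. Seriousness is also one item on the record. An event that becomes serious in Part 2 therefore carries a Part 1 onset date.
5. Same trace for a bardoxolone patient: the later peak enters the Part 1 active column, and the worsening is missed in BARD.

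**Data cut.** SAP 1.9.3 places the main Part 1 analysis after all of a cohort's patients complete Part 1. Earlier patients may then be well into Part 2, so step 2 is realistic. SAP 1.9 also allows earlier analyses, in which it may not arise.

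**Scale.** Inputs: 38 and 16 patients in Cohorts 1 and 2 at 3:1; about 24 in each of six subcohorts at 2:1 (Protocol 7.1 and 7.2). SAP 1.8 pools safety analyses into All PAH, CTD-PAH, Non-CTD PAH and All PH. Nominal placebo numbers:

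- Cohorts 1 and 2: (38 + 16) / 4 = 13.5
- Cohorts 3a and 3b: (2 × 24) / 3 = 16
- Cohorts 4a to 4d: (4 × 24) / 3 = 32
- Total: 13.5 + 16 + 32 = 61.5 of 198

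| Table | Placebo n | One placebo event |
|---|---|---|
| All PAH | 13.5 + 16 = 29.5 | 1/29.5 = 3.4 points |
| All PH | 32 | 1/32 = 3.1 points |
| One 24-patient subcohort | 24/3 = 8 | 1/8 = 12.5 points |

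The CTD and non-CTD groups each add an unstated share of the 13.5 to a base of 8, so one event is between 1/21.5 = 4.7 and 12.5 points. If every subcohort grew to 72, All PAH would have 13.5 + 48 = 61.5 placebo patients (1.6 points) and All PH 96 (1.0 point).

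**The case against.** The strongest reply is that SAP 3.5.5 does intend to count these events. A reader might infer that an event starting on placebo and worsening on bardoxolone is by design never counted in Part 2. The text does not support that: the rule includes it under PBO-BARD. What fails is the supply of data to the rule.

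A reader might also infer that the error always flatters the drug. That is not supported for Part 1. The same recording rule applies to about 198 − 61.5 = 136.5 active patients, and Cohort 3 and 4 patients may up-titrate at Week 20, another occasion for worsening. Placebo patients begin new exposure at Week 16, which makes them the particular concern, but the net direction is open.

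Other points have weight:

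- The eCRF specification sits in a data management plan and the table details in mock outputs, neither available here. Protocol 11.6 lists what collection includes; it is not a database design. A dated severity field or record splitting cannot be excluded, though 11.6 directs otherwise.
- The AE definition in Protocol 11.2.1.1 covers previous conditions that have become more severe since study drug was given. It does not say that an AE already open gets a second record.
- Fluid retention is also followed by weights, BNP and unblinded committee review, and serious events have dated follow-up forms (Protocol 11.7). These protect patients and help detect a signal. Neither document routes them into the AE tables, and the forms do not cover non-serious worsening.
- Part 2 is descriptive and the SAP calls the study exploratory. This limits the consequence; it does not make the rule workable.

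**Conclusion.** The conflict stands. Protocol 11.6 as written does not provide the data that SAP 3.5.5 needs, and together with SAP 3.4.5.1 it lets severity or seriousness reached after Week 16 appear in Part 1 tables that SAP 3.4 closes at Week 16. In Part 2 the result is an undercount of worsening in both BARD and PBO-BARD. In Part 1 it can inflate severity in either arm, depending on the data cut.

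In the pooled tables of SAP 1.8, one misplaced placebo event is about 3.4 points (All PAH) or 3.1 points (All PH). The 12.5-point figure applies where only 8 placebo patients are in the table, as in a single 24-patient subcohort. SAP 1.8 adds individual-cohort summaries only for eGFR, walk test and lung function, although SAP 3 and 3.4 speak of analyses by cohort. The misplaced grade is a severe one only if the peak was severe.

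This rests on planned sizes, nominal allocation ratios, and an eCRF that follows Protocol 11.6. The documents give no rate for events that straddle Week 16 and then worsen, so total impact cannot be stated. The repair is cheap and should be made.

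A smaller error sits in the same SAP sentence: its example moves from a severity grade to seriousness, while Protocol 11.5 grades mild, moderate and severe.

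**What to change.** 1. **Protocol 11.6 and eCRF guidance.** When an AE ongoing at the Week 16 visit increases in severity or becomes serious in Part 2, open a new AE record, worded as a worsening of the earlier event, with its own onset date, severity and seriousness. The protocol already does this for pre-existing conditions.
2. **Data already collected.** Query AEs ongoing at Week 16 against source documents, where the changes should already be noted.
3. **SAP 3.4.5.1.** For patients who enter Part 2, take Part 1 severity and seriousness only up to the Week 16 visit.
4. **SAP 3.5.5.** Identify worsening from the new records, and in the example replace serious with severe.

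Cost: guidance wording, one targeted query and a few SAP sentences. No new patient assessment is needed.
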